## **9.5 Records Retention**

For non-FDA regulated studies, summarize the record retention plan applicable to the study (taking into account any applicable NYULMC Department, Division or Research Center requirements, or applicable funding sponsor requirements.)

For FDA-regulated studies the following sample language is appropriate:

The Principle Investigator will retain study essential documents for at least 2 years after the last approval of a marketing application in their country and until there are no pending or contemplated marketing applications in their country or at least 2 years have elapsed since the formal discontinuation of clinical development of the investigational product. These documents will be retained for a longer period if required by an agreement with the sponsor.

# **10 Study Monitoring, Auditing, and Inspecting**

## **10.1 Study Monitoring Plan**

This study will be monitored according to the monitoring plan in Attachment #8. As described in Section 8.6.1, a DSMB will be established for ongoing protocol review, including data, protocol compliance, safety and efficacy data, in compliance with NIH and NYU guidelines. [name] and other research personnel report on the trial status, followed by a closed session under the direction of the DSMB chairperson, during which time the investigators and research team may be present. This will be followed by an executive session restricted to DSMB members. Issues discussed may include those related to subject safety and benefit, whether the primary study question is being answered, conflict of interest, confidentiality, and ongoing study review (including AEs, SAEs, and regulatory issues). Following each DSMB meeting, recommendations will be made by the chairperson to [name] and a final report (edited by all DSMB members) will be prepared and submitted to NIAAA, the NYUMC IRB, and (if required) the FDA. Stopping the trial due to safety concerns or interim analysis of the primary outcome are not anticipated; the medication is FDA-approved, its use in this trial is consistent with their FDA labeling, and no significant safety issues have arisen in national post-marketing use.

## **10.2 Auditing and Inspecting**

The investigator will permit study-related monitoring, audits, and inspections by the IRB/EC, the sponsor, government regulatory bodies, and University compliance and quality assurance groups of all study related documents (e.g. source documents, regulatory documents, data collection instruments, study data etc.). The investigator will ensure the capability for inspections of applicable study-related facilities (e.g. pharmacy, diagnostic laboratory, etc.).

Participation as an investigator in this study implies acceptance of potential inspection by government regulatory authorities and applicable University compliance and quality assurance offices.

# **11 Ethical Considerations**

This study is to be conducted accordance with applicable US government regulations and international standards of Good Clinical Practice, and applicable institutional research policies and procedures.

This protocol and any amendments will be submitted to a properly constituted Institutional Review Board (IRB) or independent Ethics Committee (EC) in agreement with local legal prescriptions, for formal

CONFIDENTIAL

This material is the property of the NYU School of Medicine and Langone Medical Center. Do not disclose or use except as authorized in writing by the study sponsor

approval of the study conduct. The decision of the IRB/EC concerning the conduct of the study will be made in writing to the investigator and a copy of this decision will be provided to the sponsor before commencement of this study. The investigator should provide a list of IRB/EC members and their affiliate to the sponsor.

The patient population being studied is at risk of transient and long-term cognitive impairment that may limit potential subjects' ability to consent and benefit from this study. Individuals with AUDs often receive their care exclusively in EDs, where referrals for substance use are rarely initiated, resulting in significant healthcare costs and diminished access to treatment of this and other chronic conditions. Research to develop and practically implement effective interventions is even less common, particularly in those with severe AUDs in whom attrition and exclusion is expected. Inclusion of this patient population in study is of great significance because it may provide efficacious treatment and social stability to a population that has a disproportionate impact on healthcare and societal costs, and one that traditionally does not seek or receive care in medical settings offering addiction treatment. It has the potential to transform revolving door ED visits into an effective point of public health intervention and to incorporate the ED and its unique populations into a more integrated healthcare system.

All subjects for this study will be provided a consent form describing this study and providing sufficient information for subjects to make an informed decision about their participation in this study.

See Attachment #9 for a copy of the Subject Informed Consent Form. This consent form will be submitted with the protocol for review and approval by the IRB for the study. The formal consent of a subject, using the IRB-approved consent form, must be obtained before that subject undergoes any study procedure. The consent form must be signed by the subject and the investigator-designated research professional obtaining the consent. The enrollment process will be documented in the study's Subject Screening and Enrollment log.

The study investigator will use a process of informed consent that will be structured to be conducive to rational and thoughtful decision making by the subject. The PI and RA will obtain subjects' written informed consent after assessing their capacity to consent using the stringent procedures described in Section 4.3.3 and restated here:

The recruitment process will specifically address the likelihood that the subjects may have a compromised capacity to consent. Subjects will not be enrolled until clinically sober and medically stable. Subjects will be (re)assessed multiple times during their ED visit(s) as needed—and therefore will have multiple opportunities to be enrolled. We will use techniques shown to improve comprehension in informed consent procedures such as using a lower reading level, using larger typeface, quizzing and having multiple individuals providing the information. The PI will provide sensitivity training of investigators/RAs regarding difficult behaviors and limited comprehension and assessment of subject capacity to consent.

The PI/RA will assess subject's understanding of the study and capacity to consent to it using the **University of California San Diego Brief Assessment of Capacity to Consent to Research (UBACC)** (Attachment #2). The UBACC 10-item questionnaire is a 5-minute, easy-to-use, and validated tool, which we have studied in this population. It rates the basic elements of capacity (understanding, appreciation, reasoning, and ability to express a choice) to identify subjects with questionable capacity to consent to a specified research project. The UBACC assessment occurs after informing potential subjects about the study. Thus, first the RA/PI will review each page of the informed consent document with the patient, pausing to reassess comprehension throughout the process. Then, the RA/PI will administer the UBACC. Once the RA/PI confirms the subject's comprehension (with the UBACC), the RA/PI will request the patient's signature and provide the patient with a copy of the signed consent document. If, at any point during the consent process, the RA/PI does not believe the patient comprehends the study procedures the patient will not be enrolled at that time, but he or she may be eligible in the future. Patients who are not able to successfully complete ("pass") the UBACC may be further assessed by psychiatry consultation.

CONFIDENTIAL

This material is the property of the NYU School of Medicine and Langone Medical Center. Do not disclose or use except as authorized in writing by the study sponsor

In addition, the PI/RA will ask the subject to consent to being audio recorded (for qualitative interviews, counseling sessions, and quality assurance monitoring). If the subject declines to provide their written informed consent to be recorded, the subject may still participate in the study (i.e. audio recording is optional).

Subjects may be required to sign separate authorization forms for release of their personal health information to and from entities involved in their care, including care managers, case workers, housing facilitators, health providers, and government agencies/institutions. These data will be used to help coordinate and facilitate health and social needs and track outcomes. The purpose of this will be primarily clinical, rather than research. Each institution will ensure protection of PHI. All institutions, with the exception of the NYC Department of Homeless Services, are HIPAA covered entities. All Institutions will consult their respective IRBs; the NYC Fire Department Emergency Medical Services will use the IRB of the NYC Department of Health and Mental Hygiene.

Individuals who are authorized to obtain consent must be listed on the protocol. If necessary to use 'Auditor/Witness' and/or translator, these roles would be described in this section. During follow-up visits subjects capacity will be reassessed and subjects will be asked to provide assent to continue participating in the study.

## 12 Mandatory Biomarker and Genetic Testing

Whole blood (17mL) for genomic analyses will be obtained once; this will occur at enrollment typically, but may be obtained at a later visit. The 17mL of blood will be obtained from consenting subjects for genetic analysis to test predisposition to alcohol use disorders and naltrexone effect mediation (e.g. via OPRM1 genomic analysis). During the initial enrollment visit and subsequent research visits (week 0,12,24,48), 17mL of blood will be obtained for analysis of biomarkers associated with alcohol consumption and alcohol use disorders. Each blood sample will be labeled with a unique subject ID number and the visit number of the specimen obtainment. No identifiable information will be included on the specimen tubes and only the PI will have access to the list linking subjects to their ID Number assignment. Upon collection the blood specimens will be delivered to the NYULMC CBRD, where they will be stored until shipped in batches to the Medical University of South Carolina (MUSC) Laboratory for analysis. Only study team members and CBRD staff will have access to the stored specimens. Samples will be destroyed after analysis.

## 13 Inclusion of Prisoners

"Prisoner" is defined to include any individual involuntarily confined in a penal institution. The term is intended to encompass individuals sentenced to such an institution under a criminal or civil statute, individuals detained in other facilities by virtue of statutes or commitment procedures which provide alternatives to criminal prosecution or incarceration in a penal institution, and individuals detained pending arraignment, trial, or sentencing. Persons receiving care in a medical treatment setting, who are also "prisoners" as defined above, can be considered for enrollment in research only as permitted for other prisoners as subjects.

This study involves research on conditions that particularly affect prisoners as a class. These conditions include alcoholism, unstable housing, and fragmented health and social services with frequent ED use and often without other usual source of care. There are considerable data, including our own studies, describing the pattern of frequent contacts this patient population typically has with both the hospital and the criminal justice system as well as the limited coordination of services between institutions. Although medical, social services, criminal justice, and public health institutions are eager to assist this difficult, high cost and resource utilizing population, large institutions typically operate in silos, lacking the

CONFIDENTIAL

This material is the property of the NYU School of Medicine and Langone Medical Center. Do not disclose or use except as authorized in writing by the study sponsor

coordination necessary to respond cohesively and effectively to the needs of the population. These individuals are arrested typically for minor charges related to alcohol consumption (e.g. open contain, public intoxication) and unstable housing (e.g. loitering). The resulting brief periods of incarceration are unlikely to negatively impact study procedures or outcomes consequentially. Further, recurrent episodes of incarceration can be disruptive to the delivery of healthcare (e.g. missed appointments) and social services (loss of housing); thus, it is critical to learn about these challenges that specifically affect prisoners as a class in order to develop strategies to intervene more effectively.

As an extension of our preliminary work to develop and pilot a broadly defined care management intervention, this study will explore how to better address the inadequacies of current systems of care that affect prisoners. As is reflected in the primary study aim of assessing and enhancing feasibility, we will gain valuable insight into improving continuity and coordination of care of prisoners. Specifically, we will establish linkages with the NYC Department of Health-Corrections and NYC Homeless Services and their contracted agencies to coordinate care among these high users of ED, criminal justice system, and homeless services. Each institution has caseworkers designated for high-risk, high-service utilizers; we are developing a mechanism for timely communication between these institutions to allow patient/client tracking and coordinated discharge planning. For example, selected individuals could potentially be released from jail into the care of their housing outreach case-worker and brought directly to a supportive housing facility and have medical aftercare plans established prior to release. Even in the event that the study medication cannot be administered, which we do not anticipate being a problem (for the below reasons), continued study participation could benefit the subjects through enhanced continuity of care – including upon release from incarceration.

This paragraph describes which prisoners will be eligible for enrollment and under what circumstances prisoners will be withdrawn from the study. Patients on parole or probation are eligible for enrollment. Patients who are prisoners at the time of potential enrollment will NOT eligible for study entry/inclusion. Enrolled subjects who become prisoners will remain in the study.

Extensive provisions are incorporated in the study protocol to ensure adequate protections of the subjects, all of who are considered to be vulnerable. No persons who are prisoners will be eligible for enrollment. In other words, all subjects will be entering the study as non-prisoners. Thus, there is no risk of coercion of prisoners to enroll/participate in the study. All patients will have a rigorous assessment of their capacity to consent to research participation, as described in section 4.3.3. The risks involved in the research are commensurate with the risks that would be accepted by non-prisoner volunteers. There are no added safety risks should subjects become prisoners. No additional advantages accruing to a prisoner through his/her participation in the research are of such magnitude that his/her ability to weigh the risks and benefits of the research will be impaired.

As medication (XR-NTX) is being administered in this study, it is important to explicitly state that there are no additional safety concerns for subjects in the arm receiving medications should they become prisoners. This FDA-approved medication is being administered in accordance with its safe prescribing guidelines. We do not anticipate that administration of XR-NTX will be disrupted as a result of incarceration; this is because Bellevue Hospital has an existing clinic dedicated to the care of prisoners (mostly from Rikers Jail). Protocols for the transfer of prisoners from detention centers to Bellevue Hospital for clinical care have existed many years. Subjects who are prisoners will return to Bellevue Hospital for their medical management, which may include laboratory testing and XR-NTX administration. XR-NTX is not administered unless the requisite pre-administration laboratory testing is completed. Thus, if the subject is unable to return to our medical clinics for medical management and laboratory testing, then the subject will not receive the subsequent dosage of XR-NTX. There are no adverse effects associated with disrupted treatment (other than the lack of benefit provided by the medication); XR-NTX may be discontinued at any time.

Commensurate with non-incarcerated subjects, all Alcohol-MM clinical follow-up visits and Research Visits will be conducted at Bellevue Hospital Center when possible. Research assessments (Visits 5, 8, and 14) will be conducted at Bellevue when subjects return for their clinical appointments. For incarcerated subjects who will not be coming to Bellevue Hospital for an Alcohol-MM or other clinical

CONFIDENTIAL

This material is the property of the NYU School of Medicine and Langone Medical Center. Do not disclose or use except as authorized in writing by the study sponsor

reasons, we will arrange through the jail administrators for the subjects to return to Bellevue for a Research Visit. When making arrangements with prison administrators and disclosing that the prisoner is a research subject, we will not disclose the title or purpose of the study – as we have done in the past to ensure the subjects' privacy. For security reasons, subjects/prisoners will not be notified of the specific time of the visit, which will be coordinated through the jail.

As mentioned above, there are existing systems in place for New York City prisoners to receive outpatient care in Bellevue clinics that are specifically designated for prisoners. Thus, a new workflow does not need to be established. While we know the procedures and regulations for Riker's jail and New York City detention centers, it is possible that subjects will be incarcerated outside of New York City and/or in facilities that may not participate in bringing prisoners to Bellevue for care. In the event that a subject is unable or unwilling to return for an Alcohol-MM visit, this will not pose additional medication safety risks because the subject cannot receive the medication (XR-NTX) without presenting to Bellevue. If the subject is unable or unwilling to return to Bellevue for Research Visit(s), we will attempt to make arrangements with jail administrators for us to meet with the subjects at the jail or by phone to conduct the research assessments as we have done in other studies. If it is not possible to speak with a prisoner in private and without being recorded by the jail/prison, then we will remind the subject that he/she does not need to answer any questions that he/she does not wish to answer, and we will limit research assessments to include non-incriminating data only (e.g. no questions related to drug use or criminal behavior), such as healthcare utilization, medication side effects, and quality of life. This may result in not completing research assessments for some subjects. We will address how to handle the missing data with our DSMB. Our justification for retaining prisoners in the case of data not being collected is that these are important feasibility data that should be captured in this study whose goals include assessing and enhancing feasibility. Plus, the subject/prisoner may be able to participate in a subsequent research assessment (if released during study timeframe). Further, we do not anticipate encountering these difficulties (because of the aforementioned arrangements with local jails), and are including their potential in the protocol now so that we can maximize the retention of subjects and quality of data without jeopardizing the safety, privacy, or confidentiality of the subjects.

We will make sure the parole boards will not take into account a subject's participation in the research in making decisions regarding parole. Again, we will not disclose the title or purpose of the study to jail administrators. This anonymity also helps to ensure that research participation does not influence parole boards. Subjects are also informed verbally and in the written informed consent document that we will not provide input on their behalf to parole boards. We have received a Certificate of Confidentiality so that we cannot be compelled to provide testimony if subpoenaed.

If the subject is currently on parole, he or she must determine if their monitoring can include their scheduled follow-up visits to the Bellevue clinic. If these visits are not permitted, the subject will not be able to continue his or her participation in the study. As with all subjects enrolled in the study, all measures will be taken to ensure confidentiality is maintained. To protect the rights of this vulnerable patient population, study staff will only disclose the minimum amount of information required by prisoners. Study staff, for example, will never mention the title or content of the study or disclosure that a specific individual is participating in the study. Details of the nature of the research will not be shared with the staff at the jail/prison, and visits whether in person or by phone, will only be conducted if the subject's confidentiality can be maintained and no audio-taping occurs. In the event the research staff would want to conduct visits via phone, they will submit a request to have the study phone number placed on the "Do Not Record" list.

Incarcerated subjects will receive the same financial incentives for participating in the study as non-incarcerated subjects (as long as permitted by the prison, detention center, or other governing body within the criminal justice system). Depending on the prison/detention center's policies, the stipend may be provided directly to the subject, provided to the prison to retain until the subject's release, stored at the study site until the subject is released and can come retrieve it, debited to the prison commissary, paid to a relative, or mailed upon the subject's release. At the completion of the study, subjects in both arms of the study will be provided with harm reduction counseling and health care resources, including referral for alcohol-MM.

CONFIDENTIAL

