### **4.2 Exclusion Criteria**

Subjects who meet any of the following criteria will be ineligible for study enrollment:

- 1) Current physiologic dependence to opioids
- 2) Acute or chronic pain requiring opioid treatment
- 3) Acute liver injury (liver aminotransferase concentrations  $>5$  times the upper limit of normal)
- 4) Health condition considered unsafe for inclusion (at discretion of PI and/or attending physician)
- 5) Lack of capacity or willingness to consent
- 6) Currently prescribed pharmacotherapy for alcohol dependence (not including treatment of acute alcohol withdrawal syndrome)
- 7) Currently enrolled in research in which the intervention includes treatment for alcohol or substance use disorders, pharmacotherapy, or that may otherwise interfere with the study or patient safety.
- 8) Previous significant adverse reaction to naltrexone or diluent
- 9) Pregnant, nursing, or not using effective methods of birth control
- 10) Prisoners (as defined by Office of Human Research Protection) at the time of enrollment ARE NOT ELIGIBLE for study entry.
  - However, subjects who become prisoners after being enrolled will be included and not be withdrawn from the study

CONFIDENTIAL

This material is the property of the NYU School of Medicine and Langone Medical Center. Do not disclose or use except as authorized in writing by the study sponsor

- Patients on parole or probation are eligible for enrollment.

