### **4.3 Subject Recruitment and Screening**

All research will be performed on the NYU School of Medicine campus and Bellevue Hospital Center by study investigators. Recruitment will take place in the Bellevue ED (inclusive of Department of Emergency Medicine clinical and nonclinical space to ensure privacy and to minimize disruption of ongoing ED care). Follow up visits will occur in the Bellevue ED, Bellevue ambulatory care clinic, or the Clinical and Translational Science Institute Clinical Research Center. If it is only possible for subjects to conduct research assessments off site (e.g. due to mobility, health, or legal reasons), investigators may follow up with subjects off site.

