### **4.4 Early Withdrawal of Subjects**

#### **4.4.1 When and How to Withdraw Subjects**

- Subjects will be withdrawn from the study who: withdraw consent, become pregnant, develop a health condition in which XR-NTX is contraindicated (including need for opioid pain control). Abrupt termination of study treatment should not affect subject safety beyond its disease mitigating effects on alcohol dependence. Appropriate referral will be made for ongoing and/or alternative addictions treatment for all subjects withdrawn from the study.
- Subjects who are not adherent to the research protocol treatment schedule will not be withdrawn. XR-NTX administration will be allowed to resume after missed visits/injections, which is expected in this patient population due to subject-level factors such as psychosocial challenges, potential incarceration or transient medical conditions that may prevent or delay safe injection (e.g. elevation in aminotransferase elevation  $>5$  times the upper limit of normal). The window for subjects to receive XR-NTX injections will not close until the 12th month after subject enrollment. Contraindications to treatment re-initiation (opioid dependence) will be reassessed.
- To help minimize attrition and departure from protocol, we will provide incentives for subject visits, use previously piloted care coordination and subject tracking measures, and allow considerable flexibility through the pragmatic design of the study.

CONFIDENTIAL

This material is the property of the NYU School of Medicine and Langone Medical Center. Do not disclose or use except as authorized in writing by the study sponsor

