### Both Arms, Clinical Visit - Medical Management (MM) Visit (Ambulatory Care or ED)

- Subjects in both arms will be referred to Bellevue ambulatory care as scheduled for an initial visit for Alcohol-Medical Management (MM) to assess and manage adverse events, treatment effects, and support the goals of reducing the harms associated with alcohol use.
- Data will be extracted from the clinical note, including adverse events or concerns.
- Subjects in intervention arm who miss appointment will be contacted through methods described in Section 4.4.2. Follow up will be performed in the ED if subject cannot be navigated to ambulatory care. Subjects will be given a week 4 appointment.
- Subjects in the Standard Care Arm have no further clinical intervention beyond the initial referral but will have research assessments at weeks 12, 24, and 48. Any ongoing medical care will be left to the discretion of their (non-study) treating providers.

CONFIDENTIAL

This material is the property of the NYU School of Medicine and Langone Medical Center. Do not disclose or use except as authorized in writing by the study sponsor

### 6.3 Visit 3: Week 4

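### Section 13 ends participation for subjects whose parole terms rule out Bellevue clinic visits, contrary to the plan's other retention rules and its off-site assessment option

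*Combined protocol and SAP*

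**What the plan says.** Section 13 puts the burden on the subject on parole: "he or she must determine if their monitoring can include their scheduled follow-up visits to the Bellevue clinic". The consequence follows at once: "If these visits are not permitted, the subject will not be able to continue his or her participation in the study". It is participation that ends, not only attendance at the clinic.

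Other sections bear on the same subject:

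- Section 4.2: "Patients on parole or probation are eligible for enrollment". No condition on clinic access is attached.
- Section 4.2, on subjects jailed later: "subjects who become prisoners after being enrolled will be included and not be withdrawn from the study". Section 13 agrees: "Enrolled subjects who become prisoners will remain in the study". It adds that jailed subjects are kept even where assessments cannot be completed, because that is itself useful feasibility information.
- Section 4.4.1 lists withdrawn consent, pregnancy and a contraindication to the drug as reasons for withdrawal. Parole is not listed. It also states: "Subjects who are not adherent to the research protocol treatment schedule will not be withdrawn".
- Section 4.3 allows research contact away from the hospital: "If it is only possible for subjects to conduct research assessments off site (e.g. due to mobility, health, or legal reasons), investigators may follow up".
- The opening of section 6 expects incomplete procedures and does not count them as protocol violations.

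**The concern.** Two subjects who equally cannot reach the Bellevue clinic are treated in opposite ways. One held in a jail that will not transport patients to Bellevue stays in the study and may be assessed at the jail or by phone. The same person, released on parole terms that exclude the clinic, goes out altogether. Staff cannot apply the section 13 sentence and also treat the 4.4.1 list of withdrawal reasons as complete.

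Two results are at stake. Section 7.2.2 (Aim 1) reports the proportion completing the 3-, 6- and 12-month assessments, and this rule lowers that proportion by design rather than through any failure of feasibility. Section 7.3 analyses everyone randomized, so a removed subject still counts in the population but may have no interview or biomarker data after removal. Section 13 itself describes frequent contact with the criminal justice system as typical of these patients, so the situation is not far-fetched.

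**Working it through.** The plan gives no figure for this rule, so the check is mainly a comparison of sections, followed by a visit count.

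**1. Is the removal needed for follow-up?** No.
- Interviews: 4.3 permits off-site research assessment and names legal reasons. The matching sentence in section 6 omits legal reasons, a small mismatch to settle at the same time.
- Phone: section 13 provides for this, but only for incarcerated subjects. It does not yet cover a subject on parole.
- Healthcare use: 7.2.1 and 7.2.2 draw on hospital, ambulance and Medicaid records as well as self-report. The record sources need no clinic visit.
- Deaths: 3.4 and 4.4.2 use vital statistics.

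**2. When can it happen?** The post-consent eligibility checks in 4.3.4 do not ask about parole limits, and 4.2 admits subjects on parole without condition. Nothing places the question before randomisation, so the rule can operate after it.

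**3. What is collected afterwards?** Section 4.4.2 covers withdrawn consent and loss to follow-up. It does not mention removal under the parole rule. No section says that record extraction stops for such a subject, and none says that it continues.

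**4. Scheduled visits after day 0** (sections 3.1 and 6.2):

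| | Intervention | Standard care |
|---|---|---|
| Clinic visits to week 24 | week 1 + weeks 4, 8, 12, 16, 20, 24 = 1 + 6 = 7 | week 1 = 1 |
| Clinic visits with extension | 7 + weeks 28, 32, 36, 40, 44 = 7 + 5 = 12 | 1 |
| Clinic visits left after week 1 | 6 to 11 | 0 |
| Distinct weeks, research visits included | 7 + 1 = 8, or 12 + 1 = 13 | weeks 1, 12, 24, 48 = 4 |

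Weeks 12 and 24 are already intervention clinic weeks, so research visits add only week 48 in that arm.

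**5. Is this a power problem?** Section 7.1 needs 100 per arm (power 0.80) or 133 per arm (power 0.90) for a difference of 6 ED visits with SD 15. With standardised difference 6/15 = 0.40 and two-sided alpha 0.05, the two-sample t-test gives 99.1, rounded up to 100, and 132.3, rounded up to 133. Both figures reproduce. At 125 per arm the power is 0.88. The loss rates below are assumptions for illustration:

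| Assumed loss | Intervention arm only | Both arms |
|---|---|---|
| 5% | 0.87 | 0.87 |
| 10% | 0.87 | 0.85 |
| 20% | 0.84 | 0.80 |

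Power falls little. What matters is which subjects are lost and which outcomes go missing.

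**The case against.** Not every section listed is in strict contradiction. Admitting subjects on parole is compatible with a later condition on staying in. Missing treatment visits is not the same as being legally barred from them. The jail and phone route is written for prisoners and arranged with jail administrators. All of this stands. It leaves untouched the missing entry in the 4.4.1 list, the off-site allowance for legal reasons in 4.3, and section 13's own argument for keeping subjects whose data cannot be collected, which applies equally to a subject on parole.

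A reader might infer from the 7 to 12 clinic visits against 1 that the rule falls mainly on the intervention arm and so biases the comparison. The documents do not support that as a finding. The rule names no arm and is all-or-none. Both arms have a week 1 Bellevue clinic visit, so someone barred from the outset is caught in either. Research visits in both arms are planned at Bellevue, and if the phrase covers these too the count is 8 to 13 weeks against 4. Intervention visits may also take place in the ED. A visit count is not a probability of removal. What remains is conditional: a restriction that starts after week 1, or that allows only occasional visits, could affect the intervention arm more.

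It is also fair to say that the all-randomized population formally keeps the removed subject and that healthcare use need not be lost. The gap is silence about what is collected, together with the probable loss of interviews and blood samples.

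**Conclusion.** The inconsistency is real and should be resolved. As written, section 13 creates an avoidable removal, possible after randomisation, that conflicts with the plan's general policy of keeping subjects who cannot attend. It lowers a primary feasibility proportion and can leave interview and biomarker outcomes missing.

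The size is unknown. The documents give no number of subjects on parole and no rate at which clinic visits would be refused, so any count of removals would rest on invented inputs. The number may be small. An imbalance between arms is plausible under the conditions named above, but neither its existence nor its size can be established from the documents, and bias in the treatment comparison is a possibility rather than a result. The conclusion assumes only that the sentence is applied as worded.

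**What to change.** Replace the section 13 sentence with a rule for both arms:

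- A subject whose parole terms do not permit Bellevue clinic visits stays in the study for follow-up, and visits that cannot be attended are recorded as missed.
- The week 12, 24 and 48 research assessments are done off site under 4.3. The phone option in section 13 is extended explicitly to subjects on parole.
- Healthcare-use and vital-status extraction continues to the end of planned follow-up.
- All of this applies only as far as parole terms and consent permit.

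Ask about parole limits in both arms before randomisation and record the answer, so that any difference between arms can be described. Align the off-site wording in section 6 with 4.3, and state in 4.4.2 what is collected for these subjects. The change concerns follow-up only and alters no rule on giving the study drug.

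The cost is a short amendment, matched in the consent form if that repeats the rule, and a few assessments without blood samples. Off-site assessment and record extraction are already in the plan; only phone contact with subjects on parole is new.
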